5.2.2. Medication/Procedure Date Imputations

Imputation of partial start and end dates for medications/procedures is done for the purpose of classifying concomitant, pre-treatment, and baseline medications/procedures. The original values with no imputation applied will be presented in the data listings.

For medications/procedures with completely missing start dates, no imputation will be performed.

For medications/procedures with partial start dates:

- If “day” is the only missing field, impute the “day” as the first of the month.
- If “day” and “month” are the missing fields, impute the “day” and “month” to January 1.
- If only day is missing, and month and year are the same as first dose date then consider as concomitant. For a medication/procedure that is not checked as ongoing and the start date is completely missing:
 - and from the end date (either complete, partial or completely missing) it can be deduced to be prior to the first dose date of IP, then consider as pre-treatment.
 - Otherwise, consider as concomitant.

For medications/procedures with completely missing end dates and ongoing is not checked:

- End date will not be imputed, furthermore:
 - If start date is on or after Study Day 1, then consider as concomitant medication/procedure
 - If start date is prior to Study Day 1, or start date is also completely missing, then consider as pre-treatment medication/procedure
 - If start date is on Study Day 1, then consider as baseline medication/procedure

For medications/procedures with partial end dates:

- If “day” is the only missing field, and if month and year are the same as the start date and ongoing is not checked, then impute “day” as the start date “day”; otherwise impute as the last day of the month.
- If “day” and “month” are the missing fields, if year is the same as the start date and ongoing is not checked, then impute “day” and month as the start date day and start date month; otherwise impute as December 31.

For medications/procedures that have both completely missing start dates and end dates, no imputation will be made; these medications/procedures will be assumed to be concomitant.

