8.3.7. Concomitant Medication

The World Health Organization Drug Dictionary (B3 WHO Drug Global – Mar 2019) will be used to code the verbatim descriptions of prior and concomitant medications into the Anatomic Therapeutic Chemistry (ATC) classification system. Each verbatim name will be classified by anatomical main group, ATC level 1, therapeutic subgroup, ATC level 2, pharmacological subgroup, ATC level 3, and chemical subgroup, ATC level 4.

The number and percentage of subjects receiving concomitant medications will be summarized by ATC classification level 2 and level 4 for the Full Analysis set.

Pre-treatment medications will not be summarized, but will be in listings.

Baseline medications will also be summarized by ATC classification level 2 and 4.

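### In both SAPs, section 5.2.2 gives two classes to a medication with both dates missing and ongoing not checked, and calls pre-treatment a drug that was never shown to have stopped before Day 1

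*SAP*

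**What the plan says.** Section 5.2.2 (Medication/Procedure Date Imputations) has the same structure in both SAPs. Three of its rules matter here.

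- **Missing end date.** Its scope is "For medications/procedures with completely missing end dates and ongoing is not checked". Within it, a start on or after Study Day 1 gives concomitant. For the rest: "If start date is prior to Study Day 1, or start date is also completely missing, then consider as pre-treatment medication/procedure".
- **Missing start date.** Its scope is "For a medication/procedure that is not checked as ongoing and the start date is completely missing". If from the end date "it can be deduced to be prior to the first dose date of IP, then consider as pre-treatment" (the Part 1 SAP names the randomized product instead of IP). If not: "Otherwise, consider as concomitant".
- **Both dates missing.** The closing paragraph, which carries no condition on the ongoing box, says "no imputation will be made; these medications/procedures will be assumed to be concomitant".

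Section 5.7 of each SAP defines a pre-treatment medication as one that both started and stopped before Study Day 1. Section 5.9 defines a concomitant medication as one taken on any day from Study Day 1 on, including drugs begun earlier and continued. Section 5.8 defines a baseline medication as one whose period of use includes Study Day 1.

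Concomitant and baseline medications are tabulated by ATC levels 2 and 4 (Part 1 SAP 9.3.7; Part 2 SAP 8.3.7). For the remaining class, "Pre-treatment medications will not be summarized, but will be in listings".

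**The concern.** There are two separate faults.

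The first is a contradiction. A record with neither date and ongoing not checked falls under all three rules, and they do not agree. Nothing in the section says which rule wins.

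The second is a default that does not match the plan's own definition. A missing end date cannot show that a drug stopped before Day 1, yet for a drug started earlier and not checked as ongoing the rule assumes that it did. The adverse event rules in section 5.2.1 go the other way: an event is treatment-emergent unless its end date shows otherwise.

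At stake is whether a drug taken on study appears in the medication tables. This matters most in Part 2, which has no control arm. Those tables are where a reader sees background therapy summarized, and the protocol's Part 2 criteria allow stable vitamin E use and antidiabetic regimens with dose adjustments (section 4.3.2, criteria 18 and 19).

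**Working it through.** The plan states no figure to reproduce. The check applies the section 5.2.2 rules literally to every feasible pattern of dates.

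**Inputs.** Start: missing, before Day 1, on Day 1, after Day 1. End: missing, before first dose, on or after first dose. Ongoing: checked or not. Two restrictions apply: an ongoing record has no end date, and a drug started on or after Day 1 cannot end before first dose.

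**Count of feasible patterns.** A missing start allows 4 (end missing and not ongoing; end missing and ongoing; end before; end on or after). A start before Day 1 allows 4. A start on Day 1 allows 3 and a start after Day 1 allows 3. Total: 4 + 4 + 3 + 3 = 14.

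**Patterns that bear on the point.**

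| Start | End | Ongoing | Missing-start rule | Missing-end rule | Closing paragraph | Result |
|---|---|---|---|---|---|---|
| missing | missing | not checked | concomitant | pre-treatment | concomitant | conflict |
| missing | missing | checked | does not apply | does not apply | concomitant | concomitant |
| before Day 1 | missing | not checked | does not apply | pre-treatment | does not apply | pre-treatment, against 5.7 |
| before Day 1 | missing | checked | does not apply | does not apply | does not apply | concomitant by 5.9 |

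In the first row the missing-start rule gives concomitant because, with no end date, nothing can be deduced about when the drug stopped. None of the other ten patterns receives two classes. So 1 pattern in 14 is contradictory, and 1 more has a single class that the definition does not support.

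**Consequence for the third row.** Suppose a drug began before Day 1 and was stopped on Day 60, with the stop date not recorded and the box not checked. By section 5.9 it is concomitant and by section 5.8 it is a baseline medication. By section 5.2.2 it is pre-treatment, so it appears in neither summary and only in the listing.

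**Size of one record.** In Part 2, one subject of the planned 20 is 1/20 = 5% of a drug-class row. In Part 1, where the table is by treatment group, one subject is between 1/14 = 7.1% and 1/6 = 16.7% of a planned active group, and 1/19 = 5.3% of pooled placebo. A row changes only if that subject has no other qualifying record in the same ATC class.

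**The case against.** The strongest reply is that the exposure is small. Protocol section 5.6 requires start and end dates for every medication, so these records should be few, and data queries may resolve many of them. An unchecked ongoing box is some evidence that use ended. Continuing therapy should normally be marked ongoing, and then it stays concomitant. All of this stands and keeps the point minor. It does not remove it: the rule exists for the records that queries leave behind, and an unchecked box does not show that use ended before Day 1.

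A reader might infer three stronger things that the documents do not support.

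- *All background therapy without an end date drops out of the table.* It does not. The rule applies only when ongoing is not checked.
- *The section systematically removes uncertain records.* It does not. A start with only the day missing, in the month of first dose, is concomitant. A missing start whose end cannot be placed before first dose is concomitant. A partial end date outside the start's month or year is imputed to the last day of the month or to 31 December. Even for both dates missing, two of the three rules say concomitant.
- *Efficacy estimates are affected.* In the visible text, no histology, MMRM or responder analysis uses the medication class. The Part 2 SAP (section 6) adjusts for no covariates, and the only potential covariate named in the Part 1 SAP (section 6) is biopsy-confirmed NASH status.

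**Conclusion.** The point holds in both SAPs, within limits. The contradiction is certain on the wording: both dates missing and ongoing not checked leads to two classes with no precedence. The second fault is equally plain once section 5.2.2 is set beside section 5.7, but it covers only drugs with a start before Day 1, no end date and ongoing not checked.

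The effect is on the concomitant and baseline medication summaries only. Affected records remain visible in the listings. How many there will be cannot be known from the documents, so the per-record percentages show what one subject could move in a row; they do not estimate the total effect. They rest on the planned cohort sizes. This is a worthwhile tidy-up rather than a threat to any conclusion of the trial.

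**What to change.** In section 5.2.2 of both SAPs, replace the whole pre-treatment bullet with:

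*If the end date is completely missing and ongoing is not checked, classify the medication as pre-treatment only if other recorded information establishes that it stopped before Study Day 1; otherwise, including when the start date is also completely missing, classify it as concomitant.*

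Deleting only the clause about a missing start date would not be enough. It would cure the contradiction but leave the other half of the bullet at odds with section 5.7.

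The bullet also governs procedures. These are only listed (Part 1 SAP 9.3.8; Part 2 SAP 8.3.8), so they can keep a separate rule.

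The cost is one bullet in each SAP. The downside is that a few drugs that had in fact stopped before dosing may be counted as concomitant.

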5.3. Definition of Study Baseline

For study measurements (safety labs, PD, biomarkers and exploratory labs) except ALT or AST, lipids, and vital signs, each subject’s baseline value for that measurement will be defined as the latest pre-dose value. This will be determined by chronologically sorting all scheduled and

unscheduled values prior to first dose date and time and taking the latest value unless noted otherwise.

Baseline will be presented with each post-baseline change in the summary tables to allow easier review.

5.3.1. Study Baseline of ALT and AST

For ALT and AST, the baseline value will be defined as the average of all values performed during screening and Study Day 1 based on the following table. The baseline for ALT and AST are calculated and captured in the electronic Case Report Form (eCRF).

| ALT or AST Screening Assessments | | | Day 1 ALT or AST assessment | Baseline value |
|----------------------------------|---|--|--|---|
| Assessment 1 | Assessment 2 | Assessment 3 (if applicable) | | |
| Normal | Normal | Not applicable | Any | Average of Assessment 1, Assessment 2 and Day 1 (3 tests) |
| Normal | Abnormal and $\leq 40\%$ increase from Assessment 1 | Not applicable | Any | Average of Assessment 1, Assessment 2 and Day 1 (3 tests) |
| Normal | Abnormal and $>40\%$ increase from Assessment 1 | Normal or $\leq 40\%$ increase from Assessment 1 | Any | Average of Assessment 1, Assessment 2, Assessment 3 and Day 1 (4 tests) |
| Normal | Abnormal and $>40\%$ increase from Assessment 1 | Abnormal and $>40\%$ increase from Assessment 1 | Not applicable, subject excluded. | Not applicable, subject excluded. |
| Abnormal | $\leq 40\%$ increase from Assessment 1 | Not applicable | Any | Average of Assessment 1, Assessment 2 and Day 1 (3 tests) |
| Abnormal | $>40\%$ increase from Assessment 1 | $\leq 40\%$ increase from Assessment 1 | Any | Average of Assessment 1, Assessment 2, Assessment 3 and Day 1 (4 tests) |
| Abnormal | $>40\%$ increase from Assessment 1 | $>40\%$ increase from Assessment 1 | Not applicable, subject excluded. | Not applicable, subject excluded. |

5.3.2. Study Baseline for Lipids

For lipids, the baseline will be determined as the average of all pre-dose measurements within 30 days prior to Study Day 1, e.g., measurements taken at $-29 \leq \text{Study Day} \leq 1$ (Pre-dose).

5.3.3. Study Baseline for Vital Signs

For vital signs of blood pressure and pulse, measurements will be taken in duplicate starting from enrollment. Baseline for these measures should be the average of all individual assessments during screening up to Study Day 1 and prior to first dose if subject is dosed.

5.4. Definition of Duration of Exposure

The intended duration of exposure for QW dosing will be defined as the date of the last dose of IP minus Study Day 1 date plus 8 days.

5.5. Definition of Age

Age will be defined as the duration in days of date of signed informed consent or index date minus the birthdate divided by 365.25. Index date refers to specific visits if age is needed at specific visits (for example, age at specific visits will be used when deriving FIB-4 score or eGFR).

5.6. Dose Compliance

Dose compliance percentage will be the actual number of received doses divided by the expected number of doses to be received up to the end of study (EOS). Partial doses will contribute to the actual number of received doses.

5.7. Definition of Pre-treatment Medication and Pre-treatment Procedures

Pre-treatment medications are defined as any medication that start and stop being taken prior to Study Day 1.

Pre-treatment procedures are defined as any procedure that were started and completed prior to Study Day 1.

5.8. Definition of Baseline Medication

Medications that have Study Day 1 within the duration of exposure will be considered baseline medications.

5.9. Definition of Concomitant Medication and Concomitant Procedures

Concomitant medications are defined as any medication that is taken any day on or after Study Day 1. This includes medications that were started prior first dose and that were continued to be taken after Study Day 1.

Concomitant procedures are defined as any procedures that are performed any day on or after Study Day 1. This includes procedures that were started prior to first dose and that continued into Study Day 1.

5.10. Definition of the Open-Label Treatment Group

The definition of the open-label treatment group is BIO89-100 27 mg QW.

5.11. Definition of Treatment-Emergent Adverse Event

Treatment-emergent adverse events will be defined as those occurring at or after the time of the first administration of IP, e.g., first dose date and time, through study termination (EOS+28 days of reporting window), or existing prior to the time of and worsening after the time of the first administration of IP. Adverse events with onset prior to the first administration of IP that end before Study Day 1 or do not worsen after Study Day 1 will be classified as pre-treatment.

[REDACTED]

[REDACTED]

[REDACTED]

5.13. Estimated Glomerular Filtration Rate (CKD-EPI)

The eGFR will be derived using the CKD-EPI equation.

For Males:

$$\begin{aligned}
 \text{eGFR}[\text{mL/min/1.73m}^2] &= 141 \\
 &\times \min \left(\frac{\text{Serum Creatinine}[\text{mg/dL}]}{0.9}, 1 \right)^{-0.411} \\
 &\times \max \left(\frac{\text{Serum Creatinine}[\text{mg/dL}]}{0.9}, 1 \right)^{-1.209} \times 0.993^{\text{Age}[years]} \\
 &\times 1.159[\text{if black}]
 \end{aligned}$$

For Females:

$$\begin{aligned}
 \text{eGFR}[\text{mL/min/1.73m}^2] &= 141 \\
 &\times \min \left(\frac{\text{Serum Creatinine}[\text{mg/dL}]}{0.7}, 1 \right)^{-0.329} \\
 &\times \max \left(\frac{\text{Serum Creatinine}[\text{mg/dL}]}{0.7}, 1 \right)^{-1.209} \times 0.993^{\text{Age}[years]} \times 1.018 \\
 &\times 1.159[\text{if black}]
 \end{aligned}$$

5.14. Definition of Study Interruption

Study interruption will be defined as any interruption lasting ≥ 2 weeks and allowed up to 4 weeks (+4 days) that is due to any causes related COVID-19 pandemic and will require extra handling when deriving analysis visits.

5.15. Definition of Histology Outcomes

Resolution of NASH includes the total absence of ballooning (score=0) and absent or mild inflammation (score 0 to 1).

Worsening of fibrosis is defined as progression of fibrosis ≥ 1 stage in NASH CRN fibrosis score.

Fibrosis improvement is defined as ≥ 1 -stage decrease in NASH CRN fibrosis score.

Worsening of NASH is defined as increase ≥ 1 point in NAS for ballooning or inflammation.

6. Potential Covariates

There will be no adjustment for covariates.

7. Analysis Sets

The number of subjects in each analysis set will be summarized.

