
 To characterize BIO89-100 PK 	
 Maximal observed serum concentrations (C_{max}) within a dosing interval Area under the serum drug concentration by time curve within a dosing interval ($AUC_{0-\tau}$) Time to achieve C_{max} (t_{max}) Terminal elimination half-life ($t_{1/2}$) 
Additional PK parameters may be calculated if deemed appropriate.
 
The serum concentration-time data may also be used for population PK modeling with the results reported separately from the clinical study report.

Secondary	

¹ Resolution of NASH includes the total absence of ballooning (score=0) and absent or mild inflammation (score 0 to 1) associated with at least a 2 point reduction in NAS, and no worsening of fibrosis (progression ≥ 1 stage).

Objectives	Endpoints

 • To evaluate the immunogenicity of BIO89-100 as measured by presence of anti-drug antibodies (ADA) 	
 • Assessment of the incidence and characteristics of ADA after dosing (e.g., titer and/or binding specificity, to the FGF21, PEG part of BIO89-100, and neutralizing immunogenicity) • Impact of the presence of ADAs on serum BIO89-100 concentrations and clinical safety 
Additional ADA assessments will be performed if a severe hypersensitivity reaction (e.g., anaphylaxis) is observed.

 • To characterize biomarkers, PD profile, and biological activity of BIO89-100 administered at ascending doses and with both QW and Q2W dosing intervals • To evaluate the time, dose, and exposure relationship of BIO89-100 on biological activity, as assessed by biomarkers and PD 	
Change and percentage change from baseline in the following biomarkers/PD parameters:
 
 • Anthropomorphic measurements: 
 – Body weight • Laboratory parameters: 
 – Triglycerides – Non-high density lipoprotein (non-HDL) cholesterol – High density lipoprotein (HDL-c) – Low density lipoprotein (LDL-c) – Hemoglobin A1c (HbA1c) – Homeostatic model assessment of insulin resistance (HOMA-IR) – Liver function tests: alanine transaminase (ALT), aspartate transaminase (AST) – Adiponectin – N-terminal propeptide of type III collagen (Pro-C3) – Free fatty acids and Adipo-IR (fasting free fatty acids × fasting insulin) • Imaging measures:

Objectives	Endpoints

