	
 
– Magnetic resonance imaging – Proton density fat fraction (MRI-PDFF)
Other Safety Endpoints 	

Part 2 (Cohort 7)

Objectives	Endpoints
Primary 
 
• To evaluate the safety and tolerability of SC injections of 27 mg BIO89-100, administered weekly for 20 weeks, in subjects with biopsy-proven NASH (NAS ≥ 4, fibrosis stage F1 with high risk, F2 or F3) 
• To characterize effect of BIO89-100 on liver histology 	
 
• Frequency of AEs and SAEs 
• At least a 2-point improvement in NAFLD Activity Score (NAS) with at least a 1-point improvement in ballooning or lobular inflammation, and no worsening of fibrosis
Secondary 
 
• To characterize biomarkers, PD profile, and biological activity of BIO89-100 	Change and percentage change from baseline in the following biomarkers/PD parameters: 
 
• Anthropomorphic measurements: 
– Body weight 
• Laboratory parameters: 
– Triglycerides

Objectives	Endpoints
	
 – non-HDL cholesterol – HDL-c – LDL-c – HbA1c – Liver function tests: ALT, AST – Pro-C3 • Imaging measures: – MRI-PDFF

 • To characterize effect of BIO89-100 on liver histology 	
 • Improvement of fibrosis ≥ 1 stage without worsening of NASH • NASH resolution without worsening of fibrosis²

 • To characterize BIO89-100 PK 	
 • Trough concentration of BIO89-100
Other Safety Endpoints	

² Resolution of NASH includes the total absence of ballooning (score=0) and absent or mild inflammation (score 0 to 1) associated with at least a 2-point reduction in NAS, and no worsening of fibrosis (progression ≥ 1 stage).

Objectives	Endpoints

Overall Design

This study has 2 parts:

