4.1. Part 2 Objectives and Endpoints

Objectives	Endpoints
Primary	

 To evaluate the safety and tolerability of SC injections of 27 mg BIO89-100, administered weekly for 20 weeks, in subjects with biopsy-proven NASH (NAS ≥ 4, fibrosis stage F1 with high risk, F2 or F3) 	
 Frequency of AEs and SAEs

 To characterize effect of BIO89-100 on liver histology 	
 At least a 2-point improvement in NAFLD Activity Score (NAS) with at least a 1-point improvement in ballooning or lobular inflammation, and no worsening of fibrosis
Secondary	

 To characterize biomarkers, PD profile, and biological activity of BIO89-100 	
Change and percentage change from baseline in the following biomarkers/PD parameters:
 
 Anthropomorphic measurements: 
 Body weight Laboratory parameters: 
 Triglycerides non-HDL cholesterol HDL-c LDL-c HbA1c Liver function tests: ALT, AST Pro-C3 Imaging measures: 
 MRI-PDFF

 To characterize effect of BIO89-100 on liver histology 	
 Improvement of fibrosis ≥ 1 stage without worsening of NASH

Objectives	Endpoints
	
• NASH resolution without worsening of fibrosis⁶

• To characterize BIO89-100 PK	
• Trough concentration of BIO89-100
Other Safety Endpoints	
	
Exploratory Endpoints	
	

⁶ Resolution of NASH includes the total absence of ballooning (score=0) and absent or mild inflammation (score 0 to 1) associated with at least a 2-point reduction in NAS, and no worsening if fibrosis (progression \geq 1 stage).

Objectives	Endpoints

⁷ ≥30% relative reduction in liver fat by MRI-PDFF at D85

⁸ Resolution of NASH includes the total absence of ballooning (score=0) and absent or mild inflammation (score 0 to 1) associated with at least a 2-point reduction in NAS, and no worsening if fibrosis (progression ≥ 1 stage).

Objectives	Endpoints

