4.3. Part 2 Eligibility Criteria

4.3.1. Part 2 Inclusion Criteria

Subjects are eligible to be included in the study only if all of the following criteria apply:

Age and Gender

1. Subjects must be 21 to 75 years of age inclusive, at the time of signing the informed consent form (ICF).
2. Male or female.

Type of Subject and Disease Characteristics

3. Increased metabolic risk; subjects must have at least 2 of the following:
 - a. Central obesity: Waist circumference of >102 cm for males, >88 cm for females, or body mass index (BMI) >30 kg/m². BMI should not exceed 50 kg/m²
 - b. Fasting plasma glucose ≥ 126 mg/dL or previously diagnosed T2DM
 - c. Increased fasting triglycerides (≥ 150 mg/dL) or on treatment for hypertriglyceridemia
 - d. Reduced fasting HDL cholesterol (<40 mg/dL for male and <50 mg/dL for female)
 - e. Hypertension or treatment of previously diagnosed hypertension

Only subjects meeting Criterion 3 should be further evaluated for participation. Subjects who do not initially meet Criterion 3 may be re-tested, based on investigator judgment.

4. Evidence of fibrosis – must meet at least one of the following criteria:
 - a. Fibroscan VCTE score ≥ 8.5 kPa at screening or within the last 3 months¹⁰ AND Aspartate aminotransferase (AST) > 20 U/L for males or > 17 U/L for females in the first screening measurement¹¹
 - b. A historical liver biopsy obtained more than 24 weeks and less than 2 years before Screening with Stage 1, 2 or 3 fibrosis.
5. Evidence of steatosis by Fibroscan and MRI-PDFF:
 - a. All subjects must complete a Fibroscan with CAP measurement. Fibroscan must be done with a subject-appropriate probe during screening; CAP score should be ≥ 280 dB/m at screening or within the last 3 months unless an MRI-PDFF $\geq 8\%$ within the last 12 months is available and the current CAP score is similar to or greater than CAP score when previous MRI-PDFF was done.

NOTE: If a Fibroscan model with CAP technology is not available, MRI-PDFF will be adequate to assess steatosis.
 - b. MRI-PDFF $\geq 8\%$ at screening (MRI must be completed no more than 35 days prior to baseline)
6. Biopsy-proven NASH in a liver biopsy obtained within 24 weeks of baseline with fibrosis stage F1, F2, or F3 and NAS ≥ 4 , with a score of at least 1 in each of steatosis, ballooning degeneration, and lobular inflammation.

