4.1.2. Primary Efficacy Endpoint

The primary efficacy endpoint is:

- At least a 2-point improvement in NAS with at least a 1-point improvement in ballooning or lobular inflammation, and no worsening of fibrosis

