4.2. Secondary Endpoints

The secondary PD endpoints are:

Anthropometric measurements:

- Change from baseline and percent change from baseline in body weight over time

Laboratory parameters:

- Change from baseline and percent change from baseline in triglycerides over time
 - Change from baseline and percent change from baseline in triglycerides over time in subjects with baseline triglycerides ≥ 150 mg/dL
- Change from baseline and percent change from baseline in non-high density lipoprotein (non-HDL) cholesterol over time
- Change from baseline and percent change from baseline in high density lipoprotein (HDL-c) over time
 - Change from baseline and percent change from baseline in HDL-c over time in subjects with baseline HDL-c < 40 mg/dL for males and < 50 mg/dL for females
- Change from baseline and percent change from baseline in low density lipoprotein (LDL-c) over time
 - Change from baseline and percent change from baseline in LDL-c over time in subjects with baseline LDL-c ≥ 100 mg/dL
- Change from baseline and percent change from baseline in hemoglobin A1c (HbA1c) over time

Liver function tests:

- Change from baseline and percent change from baseline in alanine transaminase (ALT) over time
- Change from baseline and percent change from baseline in aspartate transaminase (AST) over time
- Change from baseline and percent change from baseline in n-terminal propeptide of type III collagen (Pro-C3) over time

Imaging measures:

- Change from baseline and percent change from baseline in magnetic resonance imaging – proton density fat fraction (MRI-PDFF)

Histology measures:

- Improvement of fibrosis ≥ 1 stage without worsening of NASH
- NASH resolution without worsening of fibrosis

PK measures:

- Trough concentration of BIO89-100

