8.5.7. Immunogenicity Analyses

Immunogenicity assessment will utilize a tiered approach (i.e., screen, confirm, titer, binding specificity and neutralizing activity). Results of immunogenicity assessment will be summarized by displaying the number and proportion of subjects with positive and negative tests. Antibody titers will be listed and summarized (i.e., n, mean, SD, median, min, max) by study visit.

Available binding specificity and neutralizing immunogenicity results will be listed.

9. Changes to Planned Analysis in the Protocol

There are no changes to the planned analysis in the protocol.

10. Statistical Software

All statistical analyses will be performed using SAS version 9.4 or higher.

11. References

National Heart, Lung and Blood Institute (2020). *Low Blood Pressure*. Retrieved May 19, 2020, from <https://www.nhlbi.nih.gov/health-topics/low-blood-pressure>.

12. Appendix

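### The Part 2 SAP drops the protocol's 2-point NAS reduction from the definition of NASH resolution, so a protocol non-responder can be counted as resolved

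*SAP*

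**What the plan says.** The protocol defines NASH resolution for the Part 2 secondary endpoint in three footnotes, and all three agree. Two are in the Synopsis (section 1.1). Footnote 1 adds to the ballooning and inflammation conditions that they be "associated with at least a 2 point reduction in NAS, and no worsening of fibrosis", and footnote 2 says "associated with at least a 2-point reduction in NAS, and no worsening of fibrosis". Footnote 6 in section 4.1 (Part 2 Objectives and Endpoints) again has "associated with at least a 2-point reduction in NAS", together with the fibrosis condition.

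Section 5.15 of the Part 2 SAP (Definition of Histology Outcomes) reads "Resolution of NASH includes the total absence of ballooning (score=0) and absent or mild inflammation (score 0 to 1", and its sentence on resolution ends there. It goes on to define worsening of fibrosis, fibrosis improvement and worsening of NASH, but attaches no NAS change to resolution.

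Section 4.2 of the same SAP only names the endpoint: "NASH resolution without worsening of fibrosis". Section 8.4.1.1 sends the analyst to sections 4.1.2, 4.2 and 4.4 for the response criteria and reports each as a proportion with a 95% CI. Section 9 states: "There are no changes to the planned analysis in the protocol".

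**The concern.** Section 5.15 is the only readable place in the Part 2 SAP that defines resolution. A programmer who follows it applies two score conditions plus the fibrosis condition from the endpoint name, and never tests the change in NAS. Dropping a condition can add responders but cannot remove any, so any error favours the drug.

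It also breaks a logical link between two endpoints. The primary endpoint is "At least a 2-point improvement in NAS with at least a 1-point improvement in ballooning or lobular inflammation, and no worsening of fibrosis". Every subject enters with ballooning of at least 1, so anyone who meets the protocol's resolution endpoint has at least a 1-point ballooning improvement, at least a 2-point NAS reduction and no worsening of fibrosis. Under the protocol, every resolution responder is therefore a primary responder. Under section 5.15 this is no longer guaranteed: a subject could be reported as having NASH resolution while failing the primary NAS-response endpoint.

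The result is one of two secondary histology proportions in a 20-subject open-label cohort with no control arm, where a single subject is visible in the percentage.

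**Working it through.** The documents state no figure on this point, so there is none to reproduce. The check is whether the missing condition can change a classification among eligible subjects.

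**Inputs**

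- Eligibility (Protocol 4.3.1, criterion 6): NAS of at least 4, "with a score of at least 1 in each of steatosis, ballooning degeneration, and lobular inflammation".
- SAP resolution (Part 2 SAP 5.15): final ballooning 0, final inflammation 0 or 1.
- Protocol resolution: the same, plus a NAS reduction of at least 2.
- Cohort size: 20 (Protocol 4.2). The number expected to have paired biopsies is redacted.

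**General argument, needing no component maxima**

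Write S, I and B for steatosis, inflammation and ballooning, with 0 for baseline and 1 for the end biopsy. For an SAP-resolved subject B1 = 0, so

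NAS reduction = (S0 − S1) + (I0 − I1) + B0.

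Eligibility gives B0 ≥ 1. Since I0 ≥ 1 and I1 ≤ 1, I0 − I1 ≥ 0.

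- If steatosis improves by one grade or more, the reduction is at least 1 + 0 + 1 = 2, and the two definitions agree.
- If steatosis is unchanged, the reduction is below 2 only when B0 = 1 and I0 = I1 = 1. NAS of at least 4 then requires S0 ≥ 2. Example: 2/1/1 to 2/1/0, NAS 4 to 3, a reduction of 1.
- All other disagreements need steatosis to worsen.

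The example satisfies criterion 6 and involves no worsening of any component.

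**Counting patterns**

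The SAP gives the NAS total as 0 to 8 but no component ranges. Assume steatosis 0–3, inflammation 0–3 and ballooning 0–2.

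- Eligible baselines: 3 × 3 × 2 = 18 profiles with every component at least 1, less 1/1/1 (NAS 3), leaving 17.
- SAP-resolved end states: 4 steatosis values × 2 inflammation values = 8 per baseline, so 17 × 8 = 136 pairs.
- Baseline NAS 4 (3 profiles): the reduction is below 2 when the end NAS is 3 or 4, which 3 end states give. 3 × 3 = 9.
- Baseline NAS 5 (5 profiles): this needs an end NAS of 4, which 1 end state gives. 5 × 1 = 5.
- Baseline NAS 6 or more: this would need an end NAS of at least 5, but the largest SAP-resolved end NAS is 3 + 1 = 4. None.
- Total discordant: 9 + 5 = 14 of 136, of which 12 have higher steatosis at the end.
- With end steatosis no higher than baseline: 5 × 4 + 6 × 6 + 6 × 8 = 104 pairs, of which 2 are discordant: 2/1/1 to 2/1/0 (NAS 4 to 3) and 3/1/1 to 3/1/0 (NAS 5 to 4).

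These are unweighted counts of what is possible, not expected patient frequencies.

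**Effect of one reclassified subject**

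| Subjects with paired biopsies | Shift in rate |
|---|---|
| 20 (all enrolled) | 1/20 = 5.0 points |
| 18 (assumed) | 1/18 = 5.6 points |
| 16 (assumed) | 1/16 = 6.3 points |
| 15 (assumed) | 1/15 = 6.7 points |

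For illustration at n = 20, 4 responders give 20.0% (exact 95% CI 5.7% to 43.7%) and 5 give 25.0% (8.7% to 49.1%).

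**The case against.** The best counter-argument is that the effect will be small or nil. Any one-grade improvement in steatosis makes the two definitions agree, and with stable steatosis only a subject with baseline ballooning 1 and inflammation 1 can be discordant. Protocol 2.3.3 reports significant MRI-PDFF reductions in every Part 1 dose group, with up to 88% of treated subjects reaching a 30% reduction. MRI-PDFF is not a histological steatosis grade, but unchanged or worse steatosis does look like the less likely path for this drug. The 14 of 136 figure gives equal weight to patterns in which steatosis worsens, so 2 of 104 is the more informative count. The shift per subject is simply 1/n and would apply to any misclassification.

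The consequence is also bounded. No formal power calculation was done for Part 2, and the readable text attaches no decision rule to this endpoint. NAS and its components are summarised separately, so a discordant subject could be traced and the protocol rule applied afterwards.

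Two things cannot be seen. SAP section 4.4 has no readable content, although it covers exploratory endpoints and would not normally govern one in section 4.2. The SAP cites protocol Version 5.0, and the version of the supplied protocol is not visible.

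All of this limits the likely size, and it stands to that extent. It does not remove the mismatch. Nor does the loose verb in section 5.15 help, since the protocol footnotes use the same verb and still list the NAS condition.

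**Conclusion.** The concern holds. Read literally, section 5.15 classes as resolved some eligible subjects whom the protocol does not, and section 9 does not disclose the difference. The statement in section 9 suggests a drafting omission rather than a deliberate loosening. The bias runs in one direction, upwards, and touches only the NASH-resolution endpoint; the primary endpoint keeps its own 2-point NAS rule.

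The number of affected subjects cannot be derived from the documents and may be zero. The existence of the discordant case rests only on criterion 6 and a steatosis score of 2 being possible. The pattern counts rest on the assumed component ranges, and every per-subject shift below n = 20 rests on an assumed paired-biopsy number. Confidence in the mismatch is high; no claim is made that it will materially change the result. It should still be corrected, because the endpoint would otherwise not be the one the protocol specifies.

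**What to change.** In section 5.15 of the Part 2 SAP, add to the resolution definition the requirement that NAS fall by 2 or more points from baseline, and program the section 4.2 resolution endpoint to that definition. If the team wants the looser rule as well, report it as a separately labelled row and declare it in section 9.

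The cost is one clause. All scores needed are already read at both biopsies, so nothing more has to be collected. The reported resolution rate may come out slightly lower, and every resolution responder will again be a primary responder, which gives a simple check on the programming.
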